8. SUBJECT COMPLETION AND WITHDRAWAL

8.1. Subject completion

A subject who returns for the concluding visit foreseen in the protocol is considered to have completed the study.

8.2. Subject withdrawal

Withdrawals will not be replaced.

8.2.1. Subject withdrawal from the study

From an analysis perspective, a ‘withdrawal’ from the study refers to any subject who did not come back for the concluding visit foreseen in the protocol.

All data collected until the date of withdrawal/last contact of the subject will be used for the analysis.

A subject is considered a ‘withdrawal’ from the study when no study procedure has occurred, no follow-up has been performed and no further information has been collected for this subject from the date of withdrawal/last contact.

Information relative to the withdrawal will be documented in the eCRF. The investigator will document whether the decision to withdraw a subject from the study was made by the subject's parent(s)/LAR(s), or by the investigator, as well as which of the following possible reasons was responsible for withdrawal:

- Serious adverse event.
- Unsolicited non-serious adverse event.
- Solicited adverse event
- Protocol violation (specify).
- Consent withdrawal, not due to an adverse event*.
- Moved from the study area.
- Lost to follow-up.
- Other (specify).

*In case a subject is withdrawn from the study because the subject's parent(s)/LAR(s) has withdrawn consent, the investigator will document the reason for withdrawal of consent, if specified by the subject/subject's parent(s)/LAR(s), in the eCRF.

Subjects who are withdrawn from the study because of SAEs/AEs must be clearly distinguished from subjects who are withdrawn for other reasons. Investigators will follow subjects who are withdrawn from the study as result of a SAE/AE until resolution of the event (see Section 7.4.1.2).

Adverse Event: For any subject withdrawn from study participation prior to the planned Study Termination Visit, it is important to determine if an AE was associated with the reason for discontinuing the study. This AE must be identified on the AE eCRF page by indicating "Withdrawn from study due to AE". Any ongoing AEs at the time of study withdrawal must be followed until the event has resolved, subsided, stabilized, disappeared, or until the event is otherwise explained, or the subject is lost to follow-up. Subjects who develop an SAE judged to be possibly or probably related to the study vaccine, including hypersensitivity reactions, should not receive subsequent vaccination.

Death: For any subject withdrawn from study participation due to death, this should be noted on the Study Termination eCRF page and the associated SAE that led to the death must be reported.

Withdrawal of consent: The subject's parent(s)/LAR(s) can withdraw consent for participation in the study at any time without penalty or loss of benefit to which the subject is otherwise entitled. Reason for early termination should be deemed as "withdrawal of consent" if the subject withdraws from participation due to a non-medical reason (i.e., reason other than AE).

If the subject's parent(s)/LAR(s) intend(s) to withdraw consent from the study, the investigator should clarify if the subject will withdraw completely from the study or if the subject will continue study participation for safety, or a subset of other study procedures.

If the subject's parent(s)/LAR(s) requests complete withdrawal from the study, no further study interventions will be performed with the subject.

Where applicable, if a subject's parent(s)/LAR(s) withdraw(s) consent but does not revoke the HIPAA authorization, the Sponsor will have full access to the subject's medical records, including termination visit information. If a subject's parent(s)/LAR(s) revokes only the HIPAA authorization, the Sponsor will have full access to all of the subject's medical records prior to the date and time of written revocation.

Lost to follow-up: Investigators will make an attempt to contact those subjects who do not return for scheduled visits or follow-up. For subjects who fail to show up for final visits (clinic or telephone contacts), or for 3 consecutive visits, study staff are encouraged to make at least 3 documented attempts to contact the subject by telephone and at least 1 documented written attempt to contact the subjects' parent(s)/LAR(s) to encourage the completion of study termination procedures. These efforts to contact the subject should be recorded in the source document. The termination date for the subject to be captured on the Study Termination eCRF page is the date of the last successful contact (clinic visit or telephone) with the subject.

Administrative Reason: Examples for subjects withdrawn from the study due to administrative reason can include: Sponsor decision to terminate the study, subject meeting a pre-specified withdrawal criterion, subject discontinuation for insurance issues, moving, no time, etc. This reason should be noted in the Study Termination eCRF page and any ongoing AEs at the time of study withdrawal must be followed as described above.

If the clinical study is prematurely terminated by the Sponsor, the investigator is to promptly inform the study subjects and local EC/IRB and should assure appropriate therapy and follow up for the subjects. All procedures and requirements pertaining to the archiving of study documents should be followed. All other study materials (study medication/vaccines, etc.) must be returned to the Sponsor.

For subjects who are withdrawn from the study due to receipt of an excluded medication/vaccination or due to significant protocol non-compliance, this reason should be noted in the Study Termination eCRF page.

Protocol violation (deviation): Investigators will apply due diligence to avoid protocol deviations. Under no circumstances should the investigator contact GSK or its agents, if any, monitoring the study to request approval of a protocol deviation, as no authorized deviations are permitted. If the investigator feels a change to the protocol would improve the conduct of the study this must be considered a protocol amendment, and unless such an amendment is agreed upon by GSK and approved by the IRB/EC and health authorities it cannot be implemented (see Section [5.1.1](#) and [Investigator Agreement](#)).

8.2.2. Subject withdrawal from study vaccine(s)

A ‘withdrawal’ from the study vaccine(s) refers to any subject who does not receive the complete treatment, i.e. when no further planned dose is administered from the date of withdrawal. A subject withdrawn from the study vaccine(s) may not necessarily be withdrawn from the study as further study procedures or follow-up may be performed (safety or immunogenicity) if planned in the study protocol.

Information relative to premature discontinuation of the study vaccine(s) will be documented on the Vaccine Administration page/screen of the eCRF. The investigator will document whether the decision to discontinue further vaccination/treatment was made by the subject’s parent(s)/LAR(s), or by the investigator, as well as which of the following possible reasons was responsible for withdrawal:

- Serious adverse event.
- Unsolicited non-serious adverse event.
- Solicited adverse event
- Not willing to be vaccinated
- Other (specify).

8.3. Screen and baseline failures

In the event that the individual is determined ineligible for study participation after signing the ICF, he/she is considered a screen failure. The reason for screen failure must be documented in the Screening and Enrolment log.

9. STATISTICAL METHODS

9.1. Determination of sample size

The study sample size was determined by the revised study design while maintaining an adequate study power to achieve all co-primary objectives previously discussed with CBER. The multiplicity issue was dealt with by controlling the global α at the level of 0.05 for all associated statistical hypotheses. This reduced number will also allow for enrolment of the minimum number of subjects exposed to rMenB+OMV NZ to fulfill initial Pediatric Study Plan (iPSP) commitment. The sample sizes were also calculated for the secondary objectives to evaluate the non-inferiority of RIV antigens. The evaluation will be performed by calculating the between-group differences/ratios and their 2-sided 95% CI. Therefore, no multiplicity was adjusted for the secondary objectives.

Study Sample Size Determination by Co-Primary Objectives

For the immune response to PCV13, sample size calculations were based on data from the PCV13 package insert and for the immune response to rMenB+OMV NZ sample size calculations were based on data from the previous GSK (legacy Novartis) V72P13 and V72P13E1, and from V72_56 study.

Using the procedure described in this section, the power for the study is presented in [Table 17](#). In case of 40% drop-out rate and 1200 subjects to be enrolled in a 2:1 ratio, it's assumed that 480 evaluable subjects from Group MenB+PCV and 240 evaluable subjects from Group Placebo+PCV could participate with data to the analyses. For PCV13 antigens a sample size of 240 will have approximately 99% power to show non-inferiority for all antigens. For MenB strains it's assumed that 480 evaluable samples from Group MenB+PCV will be evaluated in the analyses. With 240 per group for PCV13 antigen tests and 480 evaluable subjects from Group MenB+PCV for rMenB+OMV NZ strain tests, there is approximately 99% probability to reject all 23 null hypotheses, and to claim that the primary objectives of the study will be met according to the predefined success criteria.

Table 17 Power to Show Non-Inferiority PCV13 Co-Primary Objective and Sufficiency rMenB+OMV NZ Co-Primary Objectives

Co-Primary Objective	Power
Non-inferiority for GMCs for 13 antigens after the 3 rd vaccination	99.0%
Sufficiency for % of subjects with titers \geq LLOQ per each strain and all 4 strains combined (composite response) after the 3 rd vaccination	99.8%
Sufficiency for % of subjects with hSBA titers \geq 8 (for strains M14459, NZ98/254, M13520) and \geq 16 (for strain 96217) individually and all 4 strains combined (composite response) after the 4 th vaccination	>99.999%
Probability of rejection of all 23 null hypotheses.	98.8%

The power was estimated using simulations: 10.000 simulations per case. SAS 9.4 was used for the calculations.

A short summary on the steps of simulation is presented below, in the example of 40% drop-out. The definition for families is given in [Section 9.5.3.1](#).

In total 10.000 simulations were performed, each simulation consisted of:

- For testing Family 1, 240 normal distributed data were drawn for two groups and hence two times thirteen antigens, according to the ratio of GMC and the SD, as described below [Table 18](#). For PCV13, a GMC ratio of 0.8 was assumed. Correlation structure was made for between-antigen correlation of 0%.
- For testing Family 2 and 3, 480 normal distributed data were drawn for one single group and for the four strains, according to the GMTs (for post 3rd dose) and GMTs (for post 4th dose), as shown in [Table 19](#), and the SDs as described below [Table 18](#). Correlation structure was made for between-antigen correlation of 0%.
- Testing of Family 1: Shifted one-sided t-test was used to test the hypotheses and output the p-values (for the power calculation no center effect was assumed).

- d. P-values were compared with the Family Wise Error Rate (FWER) to conclude on whether the null hypotheses were rejected or not. FWER for Family 1 is initially set to be 1/3 of the full alpha, which is rounded to 0.017. The FWER for Family 2 is 0.033 and the initial FWER is 0 for Family 3. No multiplicity adjustment was performed within a family. Within family 1 all thirteen antigens were tested with the full FWER for family 1. If one or more test fail to reject the hypothesis for the antigen, family 1 fails. Consequently the alpha of family 1 will not be propagated (see bullet h. below).
- e. Preparing for testing Family 2 and 3, percentages were obtained by dichotomizing the normal random sets that were generated at step b, by applying the cut-off of LLOQ value for post 3rd or a cut-off of 8 (for strains M14459, NZ98/254, M13520) or 16 (for strain 96217) at post 4th. Per time point, composite endpoint was derived by looking into each subject if the titer is above the cut-off for all 4 individual strains and if it is then this subject is counted as “1”. Otherwise the subject is counted as “0”.
- f. For each of the ten percentages for rMenB+OMV NZ (4 individual strains and 1 composite endpoint at post-3rd and post-4th) the lower confidence limit was generated by fitting the binomial distribution with the percentage obtained from the previous step and alpha that has been assigned or propagated to the family. If the lower confidence limit is greater or equal to the sufficiency margin, then the null hypothesis is rejected for the single test. For Family 2 and 3, it is required to reject the null hypothesis for each and all of strain M14459, 96217, NZ98/254, M13520, and the composite endpoint to be able to claim the success of the family.
- g. Testing of Family 2: with the given FWER, if the LCL is greater or equal to 0.75 for each of strain M14459, 96217 and NZ98/254, M13520, and greater or equal to 0.65 for the composite endpoint, then Family 2 is claimed for success. The FWER for Family 2 is set up as 2/3 of the full alpha, which is rounded to 0.033.
- h. Alpha propagation between Family 1, 2 and 3 was calculated for 4 scenarios:
 - 1) If Family 1 had succeeded and Family 2 not, then propagate ½ FWER from Family 1 to Family 3 and the other ½ FWER to Family 2, and re-test Family 2 with the new FWER which is the sum of the original FWER from Family 2 plus the ½ of FWER from Family 1. If the null hypothesis were rejected during the 2nd time test, then claim the success of Family 2 and propagate full FWER to Family 3; otherwise Family 2 fails and proceed with Family 3 testing with the ½ of FWER propagated from Family 1.
 - 2) If Family 2 had succeeded and Family 1 not, then propagate ½ FWER from Family 2 to Family 3 and the other ½ FWER to Family 1, and re-test Family 1 with the new FWER which is the sum of the original FWER from Family 1 plus the ½ of FWER from Family 2. If the null hypothesis were rejected during the 2nd time test, then claim the success of Family 1 and propagate full FWER to Family 3; otherwise Family 1 fails and proceed with Family 3 testing with the ½ of FWER propagated from Family 2.
 - 3) If both Family 1 and Family 2 had succeeded, then the FWER from both families were propagated to Family 3, and proceed to test Family 3;

- 4) If both Family 1 and Family 2 had failed, then no FWER will be propagated to Family 3, and we stop the testing globally.
- i. Testing of Family 3: with the given FWER, if the LCL is greater or equal to 0.6 for each of strain M14459, 96217 and NZ98/254, M13520, and greater or equal to 0.5 for the composite endpoint, then Family 3 is claimed for success.
- j. Add a loop on top of the aforementioned steps for 10.000 times simulation, summarize the probability of have all hypotheses rejected for each and all families, and the probability to meet all the primary objectives.

Based on the immune response observed in infant data from V72P13E1 and the PCV13 package insert, the following assumptions were made for the calculations:

1. As estimate for the SD of the different antigens and strains was taken the upper 80% CI limits of the common standard deviations for the \log_{10} titers observed in GSK (legacy Novartis) study V72P13E1 and \log_{10} ELISA concentrations observed from PCV13 studies. SDs that were used in the sample size calculations are presented in the table below.

Table 18 Two-sided 80% Upper Confidence Limit of Standard Deviations

	80% UCL of SDs	
rMenB+OMV NZ strains	Post 4 th vaccination (SDs of GMT)	Post 3 rd vaccination (SDs of GMT)
M14459	0.45097	0.32193
96217	0.63454	0.36900
NZ98/254	0.53796	0.51670
M13520 ²	0.36477	0.45023
PCV13 antigen ¹	Post 3 rd vaccination (SDs of GMC)	
1	0.36629	
3	0.41572	
4	0.34261	
5	0.43567	
6A	0.39552	
6B	0.44974	
7F	0.34352	
9V	0.32548	
14	0.32445	
18C	0.33550	
19A	0.24439	
19F	0.45638	
23F	0.37567	

¹Estimated SDs for PCV13 antigens are the upper confidence limit of 2-sided 80% CI of back-calculated SDs, based on information (degree of freedom, 95% CI) provided on table 17 of *Prevnar13 Package Insert* (dated on July 2016) and assuming the underlying SDs fulfill a t-distribution.

² The assumptions for M13520 are cited from study V72_56 (205240) ad-hoc analysis on additional NHBA strains.

2. Underlying GMC ratios for each PCV13 antigens is assumed as 0.8.
3. For the sufficiency objectives, the following mean ($\log_{10}(\text{GMT})$) were used in simulation based on observed data from previous studies (studies V72P13 and V72P13E1 and V72_56):

Table 19 GMTs at One Month Post 3rd Dose and GMRs at One Month Post 4th rMenB+OMV NZ Vaccination

rMenB+OMV NZ strains	GMTs* Post 4 th vaccination	GMTs* Post 3 rd vaccination
M13520	1.41225	1.10501
NZ98/254	1.57978	1.15836
M14459	1.53148	1.26400
96217	3.06183	2.66753

*log-scale

4. The LODs and LLOQs associated with the 4-fold definition are assumed to be:

Table 20 Limits of Detection and Lower Limits of Quantitation for rMenB+OMV NZ strains

rMenB+OMV NZ strains	LOD	LLOQ
M13520	4	4
NZ98/254	4	6
M14459	3	5
96217	6	15

LOD: lower limit of detection, LLOQ: lower limit of quantitation.

Note: Other than for strain M13520, these LODs and LLOQs were cited from the latest lab assay validation report released in 2018. For strain M13520, the LOD and LLOQ are validated and cited from the latest laboratory assay validation report released in 2020.

5. That each comparison is statistically independent.

In conclusion, assuming a 40% drop-out rate in this age group, a total of 1200 subjects to be enrolled in a 2:1 ratio, which will lead to 480 subjects evaluable in Group MenB+PCV and 240 subjects evaluable in Group Placebo+PCV, there will be 99% power to conclude that:

- 13 PCV13 antigens will be shown non-inferiority of PCV13 vaccine when co-administrated with rMenB+OMV NZ vaccine, compared to PCV13 vaccine that is administered alone, at one month post 3rd vaccination
- The percentage of subjects with titers \geq LLOQ is more than or equal to 60% for strain M14459, 96217, NZ98/254 and M13520, and more than or equal to 50% for all 4 rMenB+OMV NZ strains at one month post 3rd vaccination.
- Percentage of subjects with 4-fold increase is more than or equal to 75% for strain M14459, 96217, NZ98/254 and M13520, and more than or equal to 65% for all four rMenB+OMV NZ strains, at one month post 4th vaccination.

Determination of the Immunogenicity Subsets Sizes for the Secondary Objectives:

As described in detail in [Table 9](#), due to limited serum volume available subjects will be randomly assigned to test different sets of RIV antigens. Subjects will either be assigned to subset A1, A2, A3 in Group MenB+PCV or assigned to subset B1 and B2 in Group Placebo+PCV (see Section [5.2.3](#)). The below tables ([Table 21](#) and [Table 22](#)) show the likelihood to achieve non-inferiority for each of the RIV antigens (excluding polio) with the proposed sample sizes for immunogenicity subsets.

Table 21 Non-inferiority to Each Individual Antigen (excluding polio antigens) in Pediarix and Hiberix, at One Month After 3rd Dose of rMenB+OMV NZ

Component	Endpoint	Non-inferiority Margin	Reference		# Evaluable Subjects per Immunogenicity Subset (MenB group/Placebo group)*	Power
			Difference in %/ratio (Co-ad vs routine)	% in Routine group or SD		
Diphtheria	%≥0.1IU/mL	10%	Diff=0%	99.4%	240/120	>99.9%
Tetanus	%≥0.1IU/mL	5%	Diff=0%	100%	240/120	>99.9%
PT	GMC	1.5	Ratio=0.8	SD: 0.31535	480/240	88.7%
FHA	GMC	1.5	Ratio=0.84	SD: 0.3111	480/240	98.3%
PRN	GMC	1.5	Ratio=0.83 ^b	SD: 0.43427	480/240	79.1%
HepB	%≥10.0mIU/mL	10%	diff=-2%	97.7%	120/120	93.5%
Hib	%≥0.15µg/mL	5%	diff=0% ^a	96.6%	360/240	91.2%
	%≥1µg/mL	10%	diff=0%	81.2%	360/240	86.7%

Abbreviations: SD, standard deviation; GMC, geometric mean concentrations; PT, pertussis toxin; FHA, Filamentous hemagglutinin; PRN, pertactin; HepB, Hepatitis B; Hib, Haemophilus influenzae type B; diff, difference

Note: The sources are V72P13 clinical study report and the package insert of vaccines, unless otherwise indicated.

SDs for Pertussis were taken from GSK study Hib-97.

^aSource: V72P12 CSR.

^b Source: V72P16 Table 14.2.1.14 Group B+OMV versus MenC.

* Considering an estimated drop-out rate of 40%.

Table 22 Non-inferiority to Each Individual Antigen in MMR II and Varivax, at One Month After 4th Dose of rMenB+OMV NZ

Component	Endpoint	Non-inferiority Margin	Reference		# Evaluable Subjects per Immunogenicity Subset (MenB group/Placebo group)*	Power
			Ratio (co-ad vs routine)	SD		
Measles	GMC	1.5	ratio=0.9	SD: 0.45 ^a	480/240	95.5%
Mumps	GMC	1.5	ratio=0.9	SD: 0.38 ^a	480/240	99.1%
Rubella	GMC	1.5	ratio=0.9	SD: 0.34 ^a	480/240	99.8%
Varicella	GMC	1.5	ratio=0.9	SD: 0.45 ^b	480/240	95.5%

a Reference for sample size calculation: GSK Study MMR-161.

b Reference for sample size calculation: GSK Study MMR-160.

* Considering an estimated drop-out rate of 40%.

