5.7.3. Laboratory assays

The measures of immunogenicity used in this study are standard, i.e., widely used and generally recognized as reliable, accurate, and relevant (able to describe the quality and extent of the immune response).

The immunogenicity of rMenB+OMV NZ is assessed in this study by measuring the serum bactericidal activity, which is a functional measure of the ability of antibodies, in conjunction with human complement, to kill meningococci, and is widely accepted and generally recognized as the serological surrogate of protection.

Serological testing for immunogenicity to rMenB+OMV NZ, PCV13 (*same pneumococcal serotypes panel (PCV13) will be used for subjects who received PCV20*) and the other routine vaccines will be performed at a GSK Biologicals' laboratory(ies) or in a laboratory(ies) designated by GSK Biologicals using standardized and validated procedures (refer to [Table 7](#)).

Please refer to [Appendix A](#) for a detailed description of the assays performed in the study. Please refer to [Appendix B](#) for the address(es) of the clinical laboratories used for sample analysis.

Table 7 Humoral Immunity (Antibody determination)

System	Component	Method	Kit / Manufacturer	Unit*	Cut-off*	Laboratory*	Overall testing prioritization
Serum	N Men B M13520 (NHBA) Ab*,∞	hSBA	In house	1/dil	4	Laboratory designated by GSK Biologicals	1
	N Men B NZ98/254 (PorA) Ab				4		
	N Men B M14459 (fHbp) Ab				3		
	N Men B 96217 (NadA) Ab				6		
Serum	Streptococcus pneumoniae.Polysaccharide 01 Ab.IgG	ECL	In house	µg/mL	0.08	GSK Biologicals ***	2
	Streptococcus pneumoniae.Polysaccharide 03 Ab.IgG				0.075		
	Streptococcus pneumoniae.Polysaccharide 04 Ab.IgG				0.061		

CONFIDENTIAL

205239 (MENB REC 2ND GEN-023 [V72_57])

Protocol Amendment 7 Final

System	Component	Method	Kit / Manufacturer	Unit*	Cut-off*	Laboratory*	Overall testing prioritization
Serum	Streptococcus pneumoniae.Polysaccharide 05 Ab.IgG				0.198		
	Streptococcus pneumoniae.Polysaccharide 06A Ab.IgG				0.111		
	Streptococcus pneumoniae.Polysaccharide 06B Ab.IgG				0.102		
	Streptococcus pneumoniae.Polysaccharide 07F Ab.IgG				0.063		
	Streptococcus pneumoniae.Polysaccharide 09V Ab.IgG				0.066		
	Streptococcus pneumoniae.Polysaccharide 14 Ab.IgG				0.16		
	Streptococcus pneumoniae.Polysaccharide 18C Ab.IgG				0.111		
	Streptococcus pneumoniae.Polysaccharide 19A Ab.IgG				0.199		
	Streptococcus pneumoniae.Polysaccharide 19F Ab.IgG				0.163		

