	Streptococcus pneumoniae.Polysaccharide 23F Ab.IgG				0.073		
Serum	Corynebacterium diphtheriae.Diphtheria Toxoid Ab.IgG	ELI	In-house	IU/mL	0.030	GSK Biologicals ***	10
	Clostridium tetani.Tetanus Toxoid Ab.IgG	ELI	In-house	IU/mL	0.037		11
	Bordetella pertussis.Filamentous Hemagglutinin Ab.IgG	ELI	In-house	IU/mL	2.046		4
	Bordetella pertussis.Pertussis Toxin Ab.IgG	ELI	In-house	IU/mL	2.693		4
	Bordetella pertussis.Pertactin Ab.IgG	ELI	In-house	IU/mL	2.187		4
	Poliovirus Sabin Type 1 Ab	NEU	In-house	ED50	8		12
	Poliovirus Sabin Type 2 Ab	NEU	In-house	ED50	8		14
	Poliovirus Sabin Type 3 Ab	NEU	In-house	ED50	8		13

CONFIDENTIAL

205239 (MENB REC 2ND GEN-023 [V72_57])

Protocol Amendment 7 Final

System	Component	Method	Kit / Manufacturer	Unit*	Cut-off*	Laboratory* **	Overall testing prioritization
	Hepatitis B Virus.Surface Ab	CLIA	CCI	mIU/mL	6.2		5
Serum	Haemophilus influenzae type b.Polyribosyl Ribitol Phosphate Ab	ELI*	In-house	µg/mL	0.066	GSK Biologicals ***	3
Serum	Measles Virus Ab.IgG	Luminox	In-house	mIU/mL	TBD	Laboratory designated by GSK Biologicals	8
	Rubella Virus Ab.IgG	Luminox	In-house	IU/mL	TBD	Laboratory designated by GSK Biologicals	9
	Mumps Virus Ab IgG	Luminox	In-house	AU/mL	TBD	Laboratory designated by GSK Biologicals	6
Serum	Varicella Zoster Virus Ab.IgG	ELI*	In-house	mIU/mL	97.0	GSK Biologicals** *	7

Ab: Antibody, CLIA: Chemiluminescence immunoassay, IgG: Immunoglobulin G, µg: Microgram, mL: Milliliter, 1/dilution: reciprocal of the dilution; ECL: Electrochemiluminescent Assay, ELI: enzyme-linked immunosorbent assay (ELISA), MSBA: manual human serum bactericidal assay (hSBA), NEU: neutralization assay, TBD: to be determined.

*Type of assays, the validated assay cut-offs and units might be subject to change during the course of the study (e.g. in case of requalification, revalidation or standardization, availability of assays). In case testing is done at another GSK designated laboratory, the validated assay cut-off may also need to be adapted accordingly. Any of these changes will be documented in a protocol amendment or clinical study report. The LLOQ for the meningococcal B strains are provided in [Table 20](#).

**Refer to [Appendix B](#) for the laboratory addresses.

***GSK Biologicals laboratory refers to the **Vaccines Clinical Laboratory and Assay Portfolio (Vx CL&AP)** in Rixensart, Belgium; Wavre, Belgium.

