### 5.3.2. Additional considerations

The log10-transformed antibody titers/concentrations at one month after the 3rd, pre-4th, and one month after the 4th vaccination will be analysed using an additive two-way Analysis of Variance (ANOVA) model which includes the vaccine-group effect, and a center effect. Summary tables will show adjusted geometric mean titers (GMTs) and/or geometric mean concentrations (GMCs) and adjusted ratios of GMTs / GMCs for each vaccine group.

Binary data tables will show unadjusted percentages and adjusted “between-group” differences (adjusted for center). The Miettinen and Nurminen method [Miettinen, 1985] will be applied.

Descriptive summary statistics will be provided for subgroups gender, race, ethnic origin and age group (6-8 weeks or  $\geq 8$  weeks), for the following parameters:

- GMCs for PCV at one month after the 3rd and 4th vaccination.
- Percentages of subjects with hSBA titer  $\geq$  LLOQ; for each of the 4 rMenB+OMV NZ test strains and for all strains combined, at each timepoint that a blood sample result will be available, in Group MenB+PCV and Group Placebo+PCV.
- Percentages of subjects with hSBA titers  $\geq 8$  (for strains M14459, NZ98/254, M13520) and  $\geq 16$  (for strain 96217); for each of the 4 rMenB+OMV NZ test strains and for all strains combined at one month after the 4th vaccination in Group MenB+PCV and Group Placebo+PCV.

Subgroup analyses will be performed on the FAS.

The MenB serum bactericidal assay (hSBA) limits to be applied to the analyses will be as follows:

Assay	LOD	LLOQ
M14459 (fHbp)	4	5
96217 (NadA)	6	14
NZ98/254 (PorA)	4	6
M13520 (NHBA)	4	6

Seroresponse for varicella will be defined as post-vaccination anti-VZV gE IgG concentration  $\geq 300$  mIU/mL among subjects who were seronegative (antibody concentration  $<$  assay cut-off) before vaccination. The assay cut-off will be the LLOQ = 97.0 mIU/mL (anti-gE ELISA).

Seroresponse of MMR will be defined as post-vaccination anti-measles virus, anti-mumps virus and anti-rubella virus antibody concentration  $\geq$  a protective threshold among subjects who were seronegative (antibody concentration  $<$  assay cut-off) before vaccination (MMR Luminex assay).

Thresholds and cut-off values are presented below:

	Measles (mIU/mL)	Mumps (AU/mL)	Rubella (IU/mL)
Threshold	116	296	24
Cut-off = LLOQ	29.082	189.240	1.916

### 5.3.2.1. Sensitivity analyses due to the administration of PCV20 at Visit 5

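### The SAP raises the M13520 LLOQ from 4 to 6, so the stated power for the post-dose-3 MenB co-primary (99.8%) becomes about 82% at the protocol's own settings

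*Protocol*

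**What the plan says.** The post-dose-3 sufficiency co-primary (Family 3; Protocol 9.5.3.1, SAP 5.3.1.3) requires the lower confidence limit for the percentage with hSBA at or above the LLOQ to reach 60% for each of four strains. For all four strains together it must reach 50%.

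Protocol 9.1 simulates this endpoint "by applying the cut-off of LLOQ value for post 3rd or a cut-off of 8" or 16 at post-dose 4. The LLOQs are in Table 20, introduced with "The LODs and LLOQs associated with the 4-fold definition are assumed to be": M13520 4, NZ98/254 6, M14459 5, 96217 15. Table 17 then reports 99.0% for Family 1 (PCV13), 99.8% for post-dose 3, above 99.999% for post-dose 4, and 98.8% on the line "Probability of rejection of all 23 null hypotheses". The text of the section puts the overall result as follows: "there is approximately 99% probability to reject all 23 null hypotheses, and to claim that the primary objectives of the study will be met".

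SAP 5.3.2 says: "The MenB serum bactericidal assay (hSBA) limits to be applied to the analyses will be as follows". Its table gives LLOQs of M13520 6, NZ98/254 6, M14459 5 and 96217 14. It also gives an M14459 LOD of 4, where Protocol Table 20 has 3.

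On changes of assay cut-off, the footnote to Protocol Table 7 says: "Any of these changes will be documented in a protocol amendment or clinical study report".

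**The concern.** For this endpoint the LLOQ is the responder definition. Two current documents give different M13520 values for it: the latest SAP amendment is tied to Protocol Amendment 8, and Table 20 in Amendment 8 still says 4. The Table 7 footnote also sends the reader to Table 20 for the MenB LLOQs. SAP Section 8 lists other changes from the planned analyses but not this one.

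Raising the cut-off can only lower the response rate. The composite is the exposed test, because its assumed rate is the closest to its margin. If it fails, Family 3 fails, and so does the claim that all primary objectives are met.

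**Working it through.** **Inputs (Protocol 9.1).** n = 480 evaluable in MenB+PCV; between-strain correlation 0; post-dose-3 log10 means from Table 19 and SDs from Table 18. Family 3 receives two-sided alpha 0.0167 + 0.0333 = 0.05 when Families 1 and 2 both succeed.

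**Response rates.** Rate = Φ((mean − log10 LLOQ)/SD).

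| Strain | Mean | SD | Rate, protocol LLOQ | Rate, SAP LLOQ |
|---|---|---|---|---|
| M13520 | 1.10501 | 0.45023 | 86.8% (LLOQ 4) | 76.6% (LLOQ 6) |
| NZ98/254 | 1.15836 | 0.51670 | 76.9% (6) | 76.9% (6) |
| M14459 | 1.26400 | 0.32193 | 96.0% (5) | 96.0% (5) |
| 96217 | 2.66753 | 0.36900 | about 100% (15) | about 100% (14) |
| Composite (product) | | | 64.1% | 56.6% |

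For M13520: (1.10501 − 0.60206)/0.45023 = 1.117, so Φ = 0.868. With LLOQ 6: (1.10501 − 0.77815)/0.45023 = 0.726, so Φ = 0.766.

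**Success rule.** With Clopper-Pearson limits at two-sided 0.05 and n = 480, the composite needs at least 262 responders (54.6%) and each strain at least 310.

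**The protocol's own figures.** With the Table 20 LLOQs, Family 3 power is above 99.999%. For post-dose 4 (cut-offs 8 and 16) the strain rates are 91.9%, 89.6%, 91.8% and 99.8%. The composite is 75.4%, and power at alpha 0.0333 is 99.8%. Multiplying the families gives 0.990 × 0.998 × 1.000 = 98.8%, as stated. The two sufficiency rows of Table 17 therefore appear to be swapped.

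**With the SAP LLOQs.** Each single-strain test keeps about 100% power, so the whole loss is in the composite:

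- Family 3 at alpha 0.05: 82.4% (20,000-run simulation of all five tests: 82.6%). At alpha 0.0333 it is 77.2%, and at 0.0167 it is 68.1%.
- Changing only M13520 gives the same 82.4%. Changing only 96217 (15 to 14) leaves power above 99.99%.
- All 23 hypotheses: 0.990 × 0.998 × 0.824 = 81.4%. The range is 80.8–82.5%, depending on whether the Family 1 alpha is read as one- or two-sided and on whether alpha is recycled. With the Table 20 LLOQs the same readings give 98.1–99.7%.

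**Sensitivity (the non-zero correlations and smaller SDs are assumptions).**

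| Setting, SAP LLOQs, alpha 0.05 | Composite | Family 3 power |
|---|---|---|
| Correlation 0 | 56.6% | 82.4% |
| Correlation 0.10 | 57.9% | 93.5% |
| Correlation 0.17 | 58.8% | 97.4% |
| Correlation 0.25 | 60.0% | 99.3% |
| Correlation 0, SDs 3% smaller | – | 93.3% |
| Correlation 0, SDs 5% smaller | – | 97.1% |

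**Subjects affected.** On the same model, (0.868 − 0.766) × 480 ≈ 49 subjects have an M13520 titer from 4 to below 6. About (0.641 − 0.566) × 480 = 36 change composite status.

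**The case against.** The strongest reply is that 82% is a floor. The simulation assumes no correlation between strains, and the SDs are deliberately high: "As estimate for the SD of the different antigens and strains was taken the upper 80% CI limits of the common standard deviations". Superseded Amendment 4 text in Appendix C, written for a different NHBA strain, reports between-strain correlations of roughly 0.17 to 0.45 in the predecessor studies. Over that range Family 3 power with the SAP LLOQs would be about 97% to above 99.9%. This stands as a reason not to call the trial badly underpowered. It does not rescue the printed figures, because the current protocol states its 99% at correlation 0.

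Second, the endpoint is worded as at or above the LLOQ with no number, and the protocol allows cut-offs to change. An analyst following the SAP has one operative value, and a later entry in the study report could satisfy the footnote. That is fair, but such an entry would neither reconcile the two plans before analysis nor correct the power statement.

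Third, the M13520 mean and SD come from an ad-hoc analysis of study V72_56 and might themselves shift under a revised assay limit. This also stands: the calculation holds them fixed, and the counts of 49 and 36 are model values, not observed titers.

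Fourth, Amendment 7 already speaks of 1200 enrolled subjects, so a restated power will not alter recruitment. The conflict in the responder definition remains whatever the stage of the trial.

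**Conclusion.** The concern holds. The protocol and SAP give different M13520 cut-offs for a co-primary responder. With the SAP cut-off, the 99.8%, 98.8% and approximately 99% figures do not hold at the protocol's own settings. Power is 82.4% for the post-dose-3 family and about 81–82% for all 23 hypotheses. These figures rest on the Table 18 and 19 values, n = 480, correlation 0 and full alpha reaching Family 3. They are the low end of a range that reaches 99.3% for the family at an assumed correlation of 0.25. The documents do not show which LLOQ is correct. If 4 were confirmed, power would stay near 100% and the SAP table would be the one in error.

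**What to change.** 1. Reconcile the M13520 and 96217 LLOQs between Protocol Table 20 and SAP 5.3.2 before analysis, and list the change in SAP Section 8.
2. Re-run the existing simulation with the SAP LLOQs, and restate Table 17 and both 99% sentences in Protocol 9.1. If 6 stands, that means about 82% for the post-dose-3 family and about 81–82% for all 23 hypotheses at correlation 0, with a correlation range shown.
3. Put the two sufficiency rows of Table 17 in the right order.
4. In conclusion (c) of Protocol 9.1, replace the 4-fold-rise criterion, now only a secondary endpoint, with the hSBA cut-offs of 8 and 16 that Family 2 tests.
5. Reconcile the M14459 LOD: the Table 7 row "N Men B M14459 (fHbp) Ab" and Table 20 have 3, the SAP has 4. This moves the 4-times-LOD rule of the secondary 4-fold-rise endpoint from 12 to 16. The M13520 cut-off of 4 in Table 7 is the LOD and needs no change.

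The cost is wording in both documents and one re-run of an existing program. No subjects are added, and no test, margin or alpha changes. The stated power at correlation 0 becomes less favourable if 6 stands.
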